1 INTRODUCTION

A chalazion, also known as a Meibomian gland lipogranuloma, is a cyst in the eyelid that is caused by a blocked Meibomian gland, in the upper or lower eyelid, that causes an inflammatory response. The Meibomian glands are responsible for excreting sebum and meibum that help lubricate the skin, eyelash hairs, and eyes. Chalazia are generally subacute dermal inflammations that are often uncomfortable and in rare cases can cause astigmatism that may require surgical treatment. Clinical signs and symptoms of a chalazion include swelling on the eyelid, eyelid tenderness, and irritation to the eye.

There are no current US FDA-approved products specifically to treat chalazion, however, typical treatments range from simple interventions, such as hot compresses, to more serious chalazion that require treatment with an injection of corticosteroid into edema or require surgical removal of the chalazion. Given no specific product is approved to target the chalazion in the eyelid subdermal region, off-label treatments with corticosteroid ophthalmic ointments and eye drops are common. These treatments often expose the eye to significant doses of corticosteroid and fail to adequately target the Meibomian gland, thus giving a less optimal effect and more risk of AEs like increase of IOP induced by steroid eye drops.

The anti-inflammatory and immunosuppressive effects of glucocorticoids, such as [REDACTED], rely on several molecular mechanisms, that have been elucidated by basic research (1). Three main mechanisms include direct effects on gene expression by the binding of glucocorticoid receptors to glucocorticoid-responsive elements (i.e., the induction of annexin I and mitogen-activated protein kinase phosphatase 1 [MKP-1]), indirect effects on gene expression through the interactions of glucocorticoid receptors with other transcription factors (i.e., NF- κ B and activator protein 1), and glucocorticoid receptor-mediated effects on second-messenger cascades (i.e., the PI3K–Akt–eNOS pathway). Unfortunately, because some of these mechanisms are also involved in systemic physiologic signaling rather than inflammatory signaling, the therapeutic effects of systemic glucocorticoids in inflammation are often accompanied by clinically significant side effects when given in the systemic circulation. Given that the target indication is a chalazion, targeting the application of [REDACTED] to the site of inflammation is considered the most effective approach with the least potential for systemic or ocular side effects.

The SUN-131 ([REDACTED]) TDS is designed for local delivery of a corticosteroid, [REDACTED], to the upper or lower eyelid. This TDS is specially engineered to gently adhere to the eyelid and is shaped to fit the contours of the eye. The backing and adhesives used are also designed to allow removal of the patch without causing irritation and to be flexible for adequate comfort. Thus, targeted local delivery of [REDACTED] to treat the chalazion can be achieved from this unique transdermal design without significant exposure of the active agent to the eye, as with ointment or drops. Thus, this is considered a dermal application of a

TDS to treat a local extra-ocular disease in the eyelid. The low local dose also will minimize any potential for systemic exposure and minimize exposure to the eye.

[Redacted text block]

[Redacted text block]

[Redacted text block]

[Redacted text block]

1.1 Phase 1 Clinical Evaluation of the SUN-131 TDS:

The safety and performance of the SUN-131 TDS was assessed in a single-center, randomized, double-masked, placebo-controlled Phase 1 clinical trial that included 2 parts. Part 1 evaluated a single dose application of SUN-131 TDS at 3 concentrations to evaluate safety and tolerability as compared to placebo. Part 2 evaluated multiple-dose administration of 2 concentrations SUN-131 TDS for 14 consecutive days as compared to placebo TDS.

In Part 1, adult healthy subjects were randomly assigned to receive one of the following study drug doses on both upper and lower eyelids in the right or left eye:

- SUN-131 0.2% TDS (n = 8)
- SUN-131 0.7% TDS (n = 8)
- SUN-131 1.5% TDS (n = 8)
- Placebo TDS (contralateral eye for each subject, n = 24)

Each subject was randomized to wear 2 active patches on the upper and lower eyelids of the right or left eye. Two placebo patches were worn on the upper and lower eyelid of the contralateral eye. Thus, a total of 4 patches were administered, with 2 active and 2 placebo patches on each eye. All patches were worn for 24 hours (e.g., 08:00 to 08:00 the following day). Given that clinically significant systemic levels of [REDACTED] were not expected after single application of the SUN-131 TDS, and the safety of topical clobetasol propionate creams with greater anticipated exposure did not lead to significant plasma levels, pharmacokinetic sampling was not conducted in this initial safety assessment.

In Part 2 of the study, the 2 highest strength concentrations of the SUN-131 TDS (i.e. 0.7% and 1.5%) were chosen for further evaluation through multiple-dose application. Adult healthy subjects were randomized to wear one active patch on either the upper or lower eyelid of the right or left eye daily for 14 days. A placebo patch was worn on the contralateral eyelid in the same location. The SUN-131 TDS concentrations planned for this study were:

- SUN-131 0.7% TDS (n = 8)
- SUN-131 1.5% TDS (n = 8)

- Placebo TDS (contralateral eye for each subject, n = 16)

All patches were worn for 16 ± 2 hours (approximately 16:00 to 08:00 the following day). Subjects were retained in the clinic overnight on Days 1 and 14 of this study for evaluation and pharmacokinetic sampling. Subjects on Day 1 had their patches applied by trained study personnel at the site and they were instructed on the proper technique to apply the patch at home. Limited pharmacokinetic sampling was taken prior to dosing and approximately 8, 12, and 16 hours after patch application on Days 1 and 2. On Day 14, the subject again had the patches applied by study personnel for the final day of evaluation and pharmacokinetic sampling. Pharmacokinetic sampling for Days 14 and 15 included plasma samples taken prior to dosing and approximately 8, 12, 16, and 24 hours after patch application.

In Part 1 (single-application) of this study a total of 24 subjects enrolled and received study drug and were included in the safety analysis data set for the single application. All 24 subjects who initiated the scheduled single application in Part 1 completed the study and there were no missed doses of study medication. Eleven of the dosed subjects enrolled in the single application portion of this study (Part 1) were Black (11 of 24 subjects, 45.8%), 9 were White (9 of 24 subjects, 37.5%), and 4 were Asian (4 of 24 subjects, 16.7%). Subjects ranged in age from 23 to 65 years. Among these subjects were 54.2% (13 of 24) were male and 45.8% (11 of 24) were female.

In Part 2 of this study a total of 16 subjects enrolled and received study drug and were included in the safety analysis data set for repeated application. A total of 16 subjects who initiated the scheduled repeated application in Part 2 completed the study and there were no missed doses of study medication. Seven (7) of the dosed subjects enrolled in the repeated application portion of this study (Part 2) were Black (7 of 16 subjects, 43.8%), 7 were White (7 of 16 subjects, 43.8%), and 2 were Asian (2 of 16 subjects, 12.5%). Subjects ranged in age from 24 to 58 years. Among these subjects, 18.8% (3 of 16) were male and 81.3% (13 of 16) were female. There were no statistically significant imbalances in baseline characteristics across groups in the trial.

SUN-131 TDS exhibited excellent adhesion in both the single application and multiple application dose groups. In the multiple application dose groups where subjects self-administered the SUN-131 TDS at home for 12 of 14 days, of all patches administered there were 2 events (0.4% of patch applications) where there was complete patch detachment. This includes a fall-off of a placebo TDS on Day 2 and a SUN-131 0.7% TDS on Day 2. There were 5 events of slight lifting of the study drug (score 1: < 25%) reported, of which 4 of these events were in the placebo group. There were 2 event of moderate lifting (score 2: 25% to 50%) with one in the SUN-131 1.5% TDS group on Day 15 and one in the SUN-131 1.5% TDS group on Day 4. Overall, there were 224 applications of SUN-131 TDS in the multiple administration groups (Part 2) of which there was 1 event (0.45% of applications) of fall-off, 2 events (0.9% of applications) of moderate lifting (25% to 50% lifted), and 1 event (0.45% of applications) of slight lifting (< 25%) of the patch. In comparison, there were 224 applications of placebo TDS in the multiple administration groups (Part 2) of which there was 1 event (0.45% of applications) of fall-off and 4 events (1.8% of applications) of slight lifting (< 25%) of the placebo patch.

Overall, 1 of 24 subjects (4.2%) in the single application treatment portion of the trial (Part 1) reported at least 1 treatment emergent adverse event (TEAE). The TEAE was considered mild (1 event, 4.2%) in severity. No subjects experienced TEAEs that were considered at least possibly treatment-related by the investigator. The highest percentage of subject-reported TEAEs was classified in the Medical Dictionary for Regulatory Activities (MedDRA) System Organ Class (SOC) of Eye disorders (4.2%).

Across treatment groups in the single application portion of the study (Part 1), the highest percentage of TEAEs were in the SUN-131 0.2% TDS (1 subject, 12.5%). There were no subjects who experienced a TEAE that was considered even possibly related to study medication. There were no TEAEs that were severe and no SAEs occurred in the single application portion of the study.

Overall, 3 of 16 subjects (18.8%) in the repeated application treatment groups reported at least 1 TEAE. There was a total of 5 TEAEs reports in the 3 subjects who experienced an event. A total of 1 of 16 subjects (6.3%) experienced a TEAE (eye pain) that was considered at least possibly treatment-related by the investigator. The highest percentage of subjects reported TEAEs classified in the SOC of Nervous system disorders (3 events of headache: 18.8%),

followed by Eye disorders (1 event of eye pain: 6.3%) and Musculoskeletal and connective tissue disorders (1 event of neck pain: 6.3%).

Across treatment groups in the repeated application, the highest percentage of TEAEs were in the SUN-131 0.7% TDS group (2 subjects, 25.0%), and the SUN-131 1.5% TDS group (1 subject, 12.5%).

Among events that were considered at least possibly related in the repeated application treatment, there was 1 subject (6.3%) who experienced a related TEAE (eye pain) in the SUN-131 0.7% TDS group. There were no events in the SUN-131 1.5% TDS group that were considered possibly related to study medication. There were no TEAEs that were severe and no SAEs occurred in the single application portion of the study.

There were no notable findings or changes in safety assessments including visual acuity (VA), slit-lamp biomicroscopy, IOP, skin irritation, or tolerability assessed by ocular and skin comfort questionnaires.

Overall, the SUN-131 TDS appeared to deliver adequate drug amounts to the eyelid without notable side effects, skin irritation, skin discomfort or other safety concerns. The performance of the SUN-131 TDS with regards to adhesion and drug delivery was considered excellent. The systemic exposure to [REDACTED] was well below levels considered safe after administration of topical [REDACTED]

1.2 Phase 2 Clinical Evaluation of the SUN-131 TDS:

Senju has more recently completed a Phase 2, multi-center, randomized, placebo-controlled clinical trial in adult subjects with a chalazion. Subjects were randomly assigned to receive either SUN-131 1.5% TDS or placebo TDS in a 1:1 ratio. All patches were worn for 16 ± 4 hours each day for 21 days. A total of 69 subjects were enrolled in the trial and 58 completed the trial. There were 11 subjects, 6 in the SUN-131 1.5% TDS group and 5 in the placebo TDS group, who discontinued the study for non-safety-related reasons. Of the 69 subjects enrolled, 68 received either the SUN-131 1.5% TDS or the placebo TDS and thus were evaluable for safety. A total of 35 subjects received at least one dose of active SUN-131 1.5% TDS, of which 29 subjects completed the study with all doses through Day 21. A total of 33 subjects received at least one dose of placebo TDS of which 29 subjects completed the study with all doses through Day 21.

Overall, the safety of the SUN-131 1.5% TDS was excellent with no clinically meaningful product-related adverse effects. There were no notable changes in VA, slit-lamp biomicroscopy, IOP, skin irritation or ocular and skin discomfort. Twenty-four (24) of 68 subjects (35.3%) experienced at least 1 TEAE in the study. Eight (8) subjects (11.8%) experienced TEAEs that were considered treatment-related by the investigator. The most frequently experienced TEAEs overall in the study were chalazion (3 subjects; 4.4%) and eye pruritus (3 subjects, 4.4%). Thus, the SUN-131 1.5% TDS demonstrated a good safety profile for the intended indication.

2 STUDY OBJECTIVES

To evaluate the efficacy and safety of SUN-131 1.5% TDS as compared with placebo TDS in the treatment of chalazion based on the proportion of subjects who have CR. Complete response is defined as the absence of any significant clinical signs of a chalazion, based on clinical judgment by an investigator, with possible scarring or skin defects resulting from healing of the chalazion allowed.

3 INVESTIGATIONAL PLAN

3.1 Overall Study Design and Plan

This is a multi-center, double-masked, randomized, placebo-controlled evaluation of the safety and efficacy of SUN-131 1.5% TDS as compared to placebo TDS in subjects with a chalazion. Subjects who may be enrolled will have only one eyelid having a single chalazion with a single visible granuloma, and its size $\leq 36 \text{ mm}^2$ and erythema scale score ≥ 1 .

Subjects meeting all inclusion and exclusion criteria will be centrally randomly assigned to receive one of the following treatments in the affected eyelid:

- SUN-131 1.5% TDS (n = 130)
- Placebo TDS (n = 130)

The randomization will be stratified by age group (<12 years, ≥ 12 years).

Subjects will be trained to apply the placebo TDS during screening. Subjects (or the guardian/caregiver) will apply the study drug on the study eyelid daily for 14 days. At baseline prior to application of the study drug, subjects will be assessed in both eyes for VA, slit-lamp biomicroscopy, IOP measurement, skin and ocular comfort query of the study eyelid and eye of the study eyelid, and skin irritation of study drug application site separate from the chalazion on the study eyelid. The chalazion site itself will also be assessed for erythema, pain related to the

chalazion, and the size of the chalazion by measuring the height and width of the chalazion with a caliper. A photograph of the chalazion at baseline will also be taken prior to first application of the study drug.

On Day 1, the subject may apply the first study drug in the clinic or at home depending on the anticipated schedule for study drug application for the entire treatment period. On Days 8 ± 1 and 15 ± 1 , the study drug should not be replaced with a new study drug in the morning of the visit to ensure the study drug is worn for minimum of 12 hours before removal by the investigator at the site. The subject may wear the study drug over 24 hours on these visit days if necessary. On Day 8 ± 1 , subjects should apply a new study drug after completion of evaluations to ensure the study drug is worn for minimum of 16 hours on that day. The subject can then return to their normal schedule of study drug removal and replacement.

All subjects will return to the site on Days 8 ± 1 and 15 ± 1 for evaluations. Subjects should not remove their patch on Days 8 ± 1 and 15 ± 1 prior to the clinic visit. During these visits, the subject will complete the ocular/skin comfort query for the study eyelid and eye of the study eyelid prior to removal of the patch. The study drug will then be removed by the investigator to assess the level of skin irritation of the study eyelid associated with the study drug. Adverse events, concomitant medication use, and therapy are queried. Ocular safety examinations including VA, slit-lamp biomicroscopy, and IOP measurement will be performed in both eyes. A clinical evaluation will also be performed to determine if the chalazion is still present. If the chalazion is still present, the chalazion site will also be assessed for erythema of the chalazion site itself, pain related to the chalazion in the study eyelid and eye of the study eyelid, and the size of the chalazion by measuring the height and width of the chalazion with a caliper. Subjects will provide daily self-evaluation of the study chalazion from Day 1 through Day 15.

On Day 22 ± 3 , the subject will be contacted by telephone to obtain AEs and any concomitant medications and therapy taken since the last visit.

There will be no safety data monitoring, nor any special steering or evaluation committees for this study. Data review and safety assessments will be conducted by the medical monitor periodically throughout the trial and at the study conclusion.

3.2 Rationale of the Study Design

This is a prospective multi-center, double-masked, randomized, placebo-controlled clinical trial. Subjects will be centrally randomly assigned in 1:1 ratio to receive either a SUN-131 1.5% TDS or placebo TDS on the eyelid affected by the chalazion. The primary purpose of the study is to evaluate the efficacy and safety of the SUN-131 1.5% TDS as compared with placebo TDS in the treatment of chalazion.

The use of a placebo TDS as the control allows for the proper assessment of efficacy and any ocular or dermal irritation due to the study drug materials or adhesive, as opposed to the active SUN-131 1.5% TDS.

3.3 Duration of Application Exposure

SUN-131 1.5% TDS or placebo TDS will be applied for a minimum of 16 hours and a maximum of 24 hours each day for 14 days. On Day 8 ± 1 , subjects may apply a new study drug after completion of evaluations to ensure the study drug is worn for a minimum of 16 hours each day. On Days 8 ± 1 and 15 ± 1 , the study drug should not be replaced with a new study drug in the morning of the visit to ensure the study drug is worn for a minimum of 12 hours before removal by the investigator at the site. The subject may wear the study drug over 24 hours on these visit days if necessary. On Day 8 ± 1 , subjects should apply a new study drug after completion of evaluations to ensure the study drug is worn for minimum of 16 hours on that day. The subject can then return to their normal schedule of study drug removal and replacement. Dosing should not be discontinued unless there is an AE that warrants stopping treatment. If the absence of the chalazion is observed prior to Day 14, dosing should be continued until Day 14 to ensure complete resolution of the chalazion. Complete response is defined as the absence of any significant clinical signs of a chalazion with possible scarring or skin defects resulting from healing of the chalazion allowed.

3.4 Schedule of Assessments

3.4.1 Visit 1 (Screening /Baseline: Day 1)

Subjects will sign an ICF prior to any study-specific procedures (note: Standard of Care [SoC] assessments may be done prior to signing the ICF and incorporated into the study if within the allowed screening process). Where appropriate, study subjects who are < 18 years of age should assent to enroll in the study (with age of assent to be determined by the IRB and be consistent with local legal requirements). Demographics, medical and ocular history, and any concomitant medication and therapy use will be documented. The ocular history will include any previously diagnosed ophthalmic abnormalities and ocular surgeries (including laser procedures). The subject, if female, will be tested to confirm she is not pregnant using an in-house US FDA-approved home urine pregnancy test. The presence of a chalazion will be confirmed as well as the size of the chalazion, erythema of the chalazion itself, and pain related to chalazion in the study eyelid and eye of the study eyelid as part of the screening procedure. A photograph of the chalazion at baseline will also be taken prior to first study drug application. Subjects will also be trained on study drug application at baseline to confirm their ability to apply the patch at home. Training with training patches should only be conducted on the non-study eyelids. When considering enrollment of younger children, and the chalazion is on the upper eyelid, the eyelid size with the eyes closed should be evaluated and ensure that the study drug can be applied securely.

Ocular safety examinations including VA, slit-lamp biomicroscopy, and IOP measurement in both eyes, skin irritation assessment of the skin around the chalazion, size of chalazion, erythema of the chalazion itself, pain related to chalazion, and ocular/skin comfort query of the study eyelid/eye will be obtained at baseline prior to the application of the first study drug.

Concomitant medications will also be evaluated at baseline. Adverse events will be evaluated following the first study drug application on Day 1. First study drug application may be done at the site or by the subject/caregiver at home depending on the anticipated dosing schedule.

Subjects meeting all inclusion criteria and none of the exclusion criteria will be enrolled into the study. Training will be conducted on study procedures and on the appropriate method to apply and remove the study drug. Subjects will be centrally randomly assigned in a 1:1 ratio to receive SUN-131 1.5% TDS or placebo TDS applied to the study eyelid affected by the chalazion. The randomization will be stratified by age group (<12 years, ≥12 years). Subjects will receive a 1-week supply of study drug, including backup study drug, and be instructed to wear the study drug daily for a minimum of 16 hours and a maximum of 24 hours, and gently cleanse and wipe the study eyelid and to allow it to dry for approximately 30 minutes before applying a new study drug.

Subjects will continue to apply the study drug each day on the study eyelid for the full treatment period. Subjects will record the time of study drug application, study drug removal, and any unusual events or patch adhesion issues in a daily subject diary, as well as any missed/fall-off/misapplications. Subjects will keep all used and unused study drug in a provided container and return to the sites.

3.4.2 Visits 2-3 (Treatment Period: Days 8 ± 1 and 15 ± 1)

Subjects will return to the study site on Days 8 ± 1 and 15 ± 1 prior to removal of the patch from Days 7 ± 1 and 14 ± 1. On Days 8 ± 1 and 15 ± 1, the study drug should not be replaced with a new study drug in the morning of the visit to ensure the study drug is worn for a minimum of 12 hours before removal by the investigator at the site. The subject may wear the study drug over 24 hours on these visit days if necessary. On Day 8 ± 1, subjects should apply a new study drug after completion of evaluations to ensure the study drug is worn for a minimum of 16 hours on that day. The subject can then return to their normal schedule of study drug removal and replacement. Subjects will be queried for AEs and concomitant medication use and therapy. Study drug accountability is done by collecting all of the used and unused study drug and reviewing the subject diary. Prior to removal of the patch the investigator will evaluate the patch adhesion. The investigator will remove the study drug and assess the level of skin irritation of the eyelid where the study drug was placed, excluding the site of the chalazion. The removed study drug will be placed in a provided container and retained for collection by Senju. The subject will complete an ocular and skin comfort query of the study eyelid and eye of the study eyelid. Ocular examinations for safety will be performed in both eyes, including VA, slit-lamp biomicroscopy, and IOP measurement.

The investigator will also evaluate if the study chalazion is still present. If the study chalazion is still present, erythema associated with the chalazion site itself will be assessed, the subject will be asked to assess the pain associated with the chalazion, and the size of the chalazion will be evaluated ([REDACTED]). If the investigator judges that the chalazion is not present, other evaluations of chalazion (size, pain, and erythema) will not be performed. Evaluation of the chalazion should be done by the same investigator as much as possible.

Subjects will be provided with another 1-week supply of study drug including backup study drug on Day 8 ± 1. Subjects will return the subject diary on Day 15 ± 1.

See the section on Early Exit Procedures in handling of early termination.

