3.5.1 Primary Outcome Measure

- CR of the study chalazion by Day 15 ± 1. Complete response is defined as the absence of any significant clinical signs of a chalazion, based on clinical judgment by an investigator. Scarring or skin defects resulting from healing of the chalazion are possible and allowed upon CR.

The assessment of CR should be done by the same investigator as much as possible.

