5.7 Size of the Chalazion

The size of the chalazion on the study eyelid will be evaluated by the investigator at each study visit at screening/baseline (Day 1), and at 30 minutes to 1 hour after patch removal on Days 8 ± 1 and 15 ± 1 . The size will be measured [REDACTED]

[REDACTED] The size will not be evaluated on Days 8 ± 1 and 15 ± 1 if the study chalazion is determined to be absent. This evaluation should be done by the same investigator throughout the study period as much as possible.

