5.8 Erythema of the Chalazion

The investigator will assess erythema of the chalazion on the study eyelid at each study visit at screening/baseline (Day 1), and at 30 minutes to 1 hour after patch removal on Days 8 ± 1 and 15 ± 1 . The quantitative scale for this assessment is described below (Table 3). This evaluation should be done by the same investigator throughout the study period as much as possible.

Table 3: Erythema of the Study Chalazion

Score	Score Description
0	No signs of erythema
1	Slight erythema
2	Mild erythema
3	Moderate erythema
4	Severe erythema

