5.9 Pain Associated with Chalazion Assessment

Subjects will be asked to assess the pain associated with the chalazion using a VAS. The VAS will be specific for pain associated with the chalazion by asking the following questions: “How intense is your pain associated with the chalazion in your eyelid” and “How intense is your pain associated with the chalazion in your eye”. For each question, a 100 mm VAS will be used with no numbers or hash marks. This assessment will be done at screening/baseline (Day 1), and at 30 minutes to 1 hour after patch removal on Days 8 ± 1 and 15 ± 1 . The pain will not be evaluated if the study chalazion is determined to be absent. The VAS scores will be collected electronically as part of the subject electronic diary.

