7.1.7 Determination of Sample Size

7.1.8 Methods for Handling Missing Data

The primary endpoint is defined as CR by Day 15 \pm 1. For this endpoint, if a subject has missing data at the specified time point, but is known to be a complete responder at an earlier assessment, the subject will be defined as having CR. However, a subject whose prior status is unknown will be defined to be a non-responder. Subjects with missing data at Day 8 and Day 15 will be considered non-responders. Subjects with missing data at Day 8 but with data at Day 15 will be assigned as a responder or non-responder based on their Day 15 results. Subjects who are responders on Day 8 will be considered responders for the purposes of the trial regardless of the Day 15 evaluation.

For all time-to-event endpoints, subjects who do not achieve the endpoint will be censored at the date of their last assessment.

For quantitative secondary endpoints, missing data will not be imputed.

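### The change-from-baseline tests of size, erythema and pain leave out subjects whose chalazion has cleared at that visit

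*Combined protocol and SAP*

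**What the plan says.** All references are to the combined protocol and SAP.

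- Section 3.5.3 lists change from baseline to Days 8 and 15 in size, erythema and pain as additional secondary outcomes.
- Section 3.4.2: "If the investigator judges that the chalazion is not present, other evaluations of chalazion (size, pain, and erythema) will not be performed". Section 3.1 applies the same condition: "If the chalazion is still present, the chalazion site will also be assessed for erythema of the chalazion site itself", and goes on to pain and size. Section 5.7 says size is not evaluated "if the study chalazion is determined to be absent". Section 5.9: "The pain will not be evaluated if the study chalazion is determined to be absent".
- Section 5.8 carries no such exception for erythema: "The investigator will assess erythema of the chalazion on the study eyelid at each study visit". It calls the scale quantitative, so the rules for quantitative endpoints apply to it.
- Section 7.1.5.3 tests quantitative secondary endpoints by two-sample t-test and Wilcoxon-Mann-Whitney test, two-sided at 0.05. Section 7.1.8: "For quantitative secondary endpoints, missing data will not be imputed".
- Section 7.1.1 places secondary efficacy analyses on the ITT population, that is, everyone randomized.
- For complete response (CR), Section 7.1.8 has its own rule: "Subjects who are responders on Day 8 will be considered responders for the purposes of the trial regardless of the Day 15 evaluation".

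No visible text gives a value for size, erythema or pain to a subject whose chalazion is absent.

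**The concern.** An absent chalazion is the best result a subject can have, and it is recorded at each visit (Section 5.6). The plan nevertheless treats that subject's size, erythema and pain as having no value. The subjects left in each test are chosen after randomization by the same judgement that defines the primary endpoint. If the patch works, more subjects leave the active arm than the placebo arm, and those who remain are no longer comparable. The result is not the ITT comparison that Section 7.1.1 specifies.

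Section 5.10 justifies measuring size on the ground that a lesion may shrink without resolving. A test limited to persisting lesions cannot give the randomized effect on size. At stake are three reported secondary results, which could understate, miss or reverse a real benefit.

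**Working it through.** **Step 1: who enters each test.** With no follow-up value there is no change from baseline, and neither test can use the subject. Exclusion is by visit:

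| Chalazion at Day 8 / Day 15 | Day 8 test | Day 15 test | Counted as CR |
|---|---|---|---|
| absent / absent | out | out | yes |
| absent / present | out | in | yes |
| present / absent | in | out | yes |
| present / present | in | in | no |

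**Step 2: how many remain.** The plan randomizes 130 per arm. The CR rates below are assumptions, with no dropout or recurrence. Retained n = 130 × (1 − proportion clear).

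| CR, placebo / active | Placebo retained | Active retained |
|---|---|---|
| 10% / 30% | 130 × 0.9 = 117 | 130 × 0.7 = 91 |
| 20% / 40% | 130 × 0.8 = 104 | 130 × 0.6 = 78 |
| 40% / 60% | 130 × 0.6 = 78 | 130 × 0.4 = 52 |

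**Step 3: what is estimated.** Let p be the proportion clear, C the mean change in clear subjects and N the mean change in the rest. With absent scored as size 0, an arm's mean change is pC + (1 − p)N. If C and N are the same in both arms, the difference is (p_active − p_placebo)(C − N). The present-only difference is N − N = 0. Assume a baseline area of 20 mm², N = −6 mm² and CR of 40% v 20%. The all-subject difference is then 0.20 × (−20 + 6) = −2.8 mm². A simulation of this case gave −2.8 mm² with 77% power, against 0.0 mm² and 5% rejection when clear subjects are dropped.

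**Step 4: a fuller simulation.** It has 130 per arm and two-sided 0.05. Cases (a) and (b) use 4000 trials per CR pair, case (c) 3000. Baseline area is gamma (shape 4.5, scale 4) truncated to 2–36 mm², mean 17.1, SD 7.2. In (a) and (b) smaller lesions clear more often (log-odds −0.7 per SD of area), and non-responder shrinkage has SD 30%. In (c) a lesion clears when a latent healing score passes an arm-specific threshold. Shrinkage (mean 30%, SD 30%) and pain change (mean −15 mm, SD 20) each correlate 0.5 with that score. Ranges cover the three CR pairs above.

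| Case | As planned (present only) | All subjects |
|---|---|---|
| (a) Non-responders shrink 30% in both arms; size | −0.3 mm²; favours active in about 5% | absent = 0: −2.0 to −2.4 mm²; 65–68% |
| (b) Shrink 40% active, 30% placebo; size | power 46–66% | absent = 0: 91–97% |
| (c) Lesions nearest healing clear first; size | +0.7 to +0.9 mm² against active; significant in the wrong direction in 13–16%, in favour in under 1% | absent = 0: 51–54% in favour |
| (c) Same, pain (Wilcoxon) | +2.9 to +3.2 mm against active; wrong direction in 14–21% | absent ranked best: 52–76% in favour |

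The reversal in (c) depends on the correlation. At 0.25, significant wrong-direction results fall to about 6–8%, where chance gives 2.5%. At 0 they do not exceed chance, but the planned pain test favours active in only 2–3% of trials, against 81–85% with absent ranked best.

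At CR of 20% placebo and 25% active little is lost: (a) 2.5% v 9%; (b) 57% v 58%; (c) pain wrong direction 5%, and 8% in favour with best rank.

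**Step 5: a second set of assumptions.** Baseline area is about 20 mm² (SD 6), with 3000 trials and CR of 40% active v 20% placebo. Besides the Step 3 case:

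- Active shifts the whole size distribution: −4.1 mm² and 97% power with absent = 0, against −2.9 mm² and 68% with clear subjects dropped.
- The lesions that shrink most are exactly the ones cleared: −1.8 mm² with absent = 0, against +1.8 mm² with clear subjects dropped, rejecting in 66%.

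With equal latent distributions and CR of 30% in both arms, the present-only test rejected in 4.5%. The fault is bias when CR rates differ, not a general inflation of type I error.

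**The case against.** **A size rule may be redacted.** Text is blacked out beside the size assessment in Sections 3.4.2, 3.5.3 and 5.7, and the key secondary text cannot be seen. This stands, so the size limb is conditional. It does not help pain: Section 5.9 shows no redaction, and the sentence in Section 7.1.8 makes no exception.

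**Dropping is inferred.** No sentence calls a skipped assessment missing data, and a zero could be derived from the presence item. That is possible, but no visible text says so, and exclusion is the literal reading of Sections 3.4.2, 7.1.5.3 and 7.1.8 together.

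**The erythema conflict is minor.** Section 5.7 also speaks of each visit before stating its exception, so Section 5.8 may simply lack a cross-reference. That is a fair reading; the wording still needs to agree.

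**The size of the bias is assumed.** This stands. The documents bound neither the CR gap nor the correlation, the reversal needs a fairly strong correlation, and the power regained in case (a) largely re-tests CR. That the comparison is selected on outcome needs none of these figures.

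**Only secondary outcomes are touched.** This also stands, and it limits the consequence.

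**Zero for size but not for pain looks uneven.** Tenderness or redness can outlast a lesion, whereas an absent lesion leaves nothing to measure with a caliper. CR does rest on a judgement about significant signs, so a trace could remain; a best-rank analysis of size would not depend on an exact zero.

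**Conclusion.** The concern holds. Followed as written, the visible plan excludes from each size, erythema and pain test the subjects who are clear at that visit, and so departs from its own ITT statement. Confidence is highest for pain. For erythema the conclusion follows from Sections 3.1 and 3.4.2, subject to reconciling Section 5.8. For size it is conditional on the redacted text.

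Under assumed CR gaps of 20 points, the planned size comparison ranges from diluted to absent to reversed; with a 5-point gap the loss is small. All CR rates, lesion sizes, pain values and correlations behind these figures are assumptions. The primary analysis is not affected. The point is worth correcting before unmasking, because the three secondary results would otherwise be reported as randomized comparisons when they are not.

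**What to change.** In Section 7.1.8, state that a chalazion recorded as absent at a visit is an observed outcome, not missing data, and apply this by visit.

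1. **Size:** use 0 mm² at that visit.
2. **Erythema and pain:** do not assume 0 in the main analysis, because CR allows residual findings (Section 3.5.1: "Scarring or skin defects resulting from healing of the chalazion are possible and allowed upon CR"). Choose one:
   - (i) rank absent-chalazion subjects as best outcomes in the Wilcoxon-Mann-Whitney test already planned, and name that the main test; or
   - (ii) score both at the existing Day 8 and Day 15 visits whether or not the chalazion is present, amending Sections 3.1, 3.4.2 and 5.9. The pain questions would then need wording that does not presuppose a chalazion.
3. **Sensitivity:** a zero-filled analysis of erythema and pain can be added.
4. **Remaining data:** leave only truly missed visits unimputed, and label any present-only comparison descriptive.
5. **Consistency:** make Sections 3.4.2 and 5.8 agree on erythema.

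**Cost.** Item 1 and option (i) need analysis wording only. They use the presence item already collected and should be settled before unmasking. Option (ii) adds one erythema grade and two pain scales at visits already held, with a change to the form logic before the first Day 8 visit.
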